Appendix 2 – Diabetic Foot Ulcer Scale – Short	
	Quality Control and Quality Assurance. Training

Celliant Clinical Trial Protocol
PI: [name]
Protocol #: HGX2020-01

Primary Study Contacts

UT Southwestern Medical Center, Department of Plastic Surgery

Principal Investigator	[name]
email	[contact]
[contact]

Parkland Hospital, Department of Plastic Surgery

Principal Investigator	[name]
email	[contact]
[contact]

Executive Summary

Title of Study Study to Evaluate Celliant Diabetic Medical Socks to Increase Tissue Oxygenation

and Incidence of Complete Wound Closure in Diabetic Foot Wounds

Protocol Number HGX2020-01

Study Purpose The purpose of this study is to demonstrate that the use of Celliant Socks

increases tissue oxygenation (via oxygen saturation, StO₂) and incidence of wound closure in subjects with diabetic foot ulcers. This study will use hyperspectral imaging and wound assessment to measure these outcomes.

Study Design This study is a prospective, multicenter, double-blind, 1:1 randomized clinical trial.

Enrollment The study will enroll 254 evaluable subjects total, 127 per arm to meet the Primary

Endpoint. Enrollment may continue up to twenty-five hundred (2500) evaluable subjects total to meet the Key Secondary Endpoint of complete wound closure.

Investigational UT Southwestern, Department of Plastic Surgery Sites Parkland Hospital, Department of Plastic Surgery

Study Duration Up to 28 weeks (including run-in and followup phase)

Efficacy EndpointsPrimary Endpoint: To compare the percent change from baseline in tissue oxygenation in Celliant and Control treated groups 12 weeks post initial application,

as measured by hyperspectral imaging.

Key Secondary Endpoint: To compare the incidence of complete wound closure of Celliant and Control treated groups 12 weeks post initial application.

Other Secondary Endpoints:

 Change in pain assessment as reported using the Visual Analog Scale (VAS)

- 2. 3-month follow-up to assess wound closure and reoccurrence
- 3. Accelerated wound closure as measured by changes in wound area, depth and volume.
- 4. Assessment of Compliance
- 5. Outcomes of Diabetic Foot Ulcer Scale Short Form
- 6. Study related AE/SAEs

Safety Endpoints The incidence of events reported

Study Groups

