Regulatory Authorities (e.g. Food and Drug Administration	Audit clinical trial for Subject protection and data integrity
Investigator/Site Staff	Collection and assessment of data for accuracy and completeness

Alternatives to Participation

Subjects are not required to participate in this research study. As an alternative to study participation, subjects will receive wound care treatment per physician discretion.

1. Trial Objectives

The objective of this trial is to evaluate percent change from baseline in tissue oxygenation (via oxygen saturation, S_tO_2) in Celliant and Control treated groups 12 weeks post initial application, as measured by hyperspectral imaging in 254 evaluable patients total when a Celliant® Diabetic Medical Sock (n=127) is worn over the patients dressing as compared to wearing a Control Medical Sock (n=127). Enrollment may include up to 2500 total subjects to meet the Key Secondary Endpoint. The Key Secondary Endpoint is to compare the incidence of complete wound closure of Celliant and Control treated groups 12 weeks post initial application*. Other secondary outcomes include wound evaluation at 3 months post complete wound closure, accelerated wound closure as measured by changes in area, depth and volume as well as treatment compliance and assessment of pain reduction.

*if the study wound is deemed closed on the week 12 visit, the patient will continue using the sock and the wound will be evaluated on week 14 to confirm healed state.

2. Selection and Withdrawal of Subjects

Inclusion Criteria:

- Diagnosis of diabetes mellitus
- Subject is willing and able to wear a sports-style tube sock at least 22 hours a day.
- Ankle Brachial Index (ABI) ≥0.5 (bedside ABI is acceptable for screening purposes as the formal imaging ABI may not be resulted prior to surgery) or toe pressure of ≥30mmHg
- One or more diabetic foot ulcers (only one will be treated) that are located in the ankle area or below that has persisted a minimum of 30 days prior to the Screening visit
- Diabetic Foot Ulcers ≥0.5cm² and ≤16cm²
- Ulcer grade I or II, Stage A, I or II Stage B, according to University of Texas Wound Classification System
- 22 years of age or older

Exclusion Criteria:

- Subject has untreated osteomyelitis
- Ulcers within 5cm of target ulcer or connected by fistulas
- Ulcer has decreased by 30% or more at the end of the run-in period
- Subject has active untreated cellulitis
- Subject has active untreated charcot

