Internal audits are done periodically to assure regulations, guidelines and protocols are adhered to appropriately. Patient binders are reviewed for proper informed consent process documentation, case report forms are compared to the source documents and reviewed for accuracy and an independent review of the inclusion and exclusion criteria using a checklist. Additionally, the use of an auditing and monitoring tool which includes sections on consent, HIPAA, on study/treatment, off treatment/off study and a general section. Weekly meetings occur to go over each study. If there are any issues that arise, they are brought up and discussed at the meeting.

4. Statistical Analyses

General Statistical Considerations

This study is a prospective, sham-controlled, subject and evaluator blinded, 1:1 randomized, multicenter clinical study. The duration of the study is up to four months for randomized subjects. Sample size may not be reduced less than the expected total enrollment of 254 evaluable subjects total but may increase up to a total of 2500 evaluable subjects. Sample size will increase based on actual attrition that is expected to be between 5 and 15%.

The purpose of this study is to evaluate safety and efficacy outcomes related to the Celliant Sock (CS). The p-value thresholds for determining statistical significance are 0.05 and 0.025 for 2- and 1-sided tests, respectively, unless otherwise specified.

Protocol #: HGX2020-01

Data will be presented using summary statistics. For example, continuous data may be displayed with the mean, median, minimum, maximum, and/or standard deviation, while categorical data may be displayed as proportions and counts.

Any changes to the analysis of the trial data will be documented either in a future protocol amendment or in the SAP.

Randomization

Randomization will be conducted in a 1:1 ratio of the Treatment Group (Celliant Sock, n=127) or to a sham Control Group (placebo sock, n=127). Randomization will be performed within randomly selected block sizes of 3 and 6 with equal probability of group assignment stratified by study center and wound size (greater than size of 4 cm²).

A Sponsor-designated independent statistical consultant will provide the randomization list. Sponsor personnel directly involved in the management, conduct, and reporting of the study will not have access to randomization assignments until the study is completed.

Analysis Population

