The primary population for the effectiveness analyses will be the intent-to-treat (ITT) population, which will include all randomized subjects regardless of whether the socks were ever worn. Subjects will be assessed to the group to which they were randomized, regardless of whether they were provided the wrong socks.

A secondary population for effectiveness analyses will be the (AT) population, including subjects that attempted to put on the sock for any amount of time. These subjects will be analyzed according to the type of socks (Celliant or Placebo) they received. This population is also the safety population, which is the population used for all safety analyses.

A third population is the modified full analysis set (mFAS), which consists of all subjects that report wearing the sock as directed for at least 10 days.

Sample Size Justification

Assuming a 2-sided alpha at 0.05, and a power of 0.85, the true mean difference at 12 weeks between groups in percent change in tissue oxygenation as measured by hyperspectral imaging is estimated to be 8.2 with a standard deviation of 21.7. At a 1:1 allocation of experimental to control subjects, a total of 254 evaluable subjects are required. The sample size will increase to account for attrition at Week 12.

Analyzing the sample size for the key secondary endpoint of incidence of complete wound closure suggests a much large trial is need. Specifically, at 2500 evaluable total subjects, there would be approximately a power of 0.85 to detect a difference in incidence of complete wound closure at 12 weeks if the expected incidence of complete wound closure was 25% in the experimental group, and 20% in the control group, an absolute difference of 5% between the experimental group and the control group.

Primary Efficacy Analyses

The primary efficacy endpoint is an inferential test of whether the Treatment Group (Celliant[®] Diabetic Medical Sock) percent change in tissue oxygenation (via oxygen saturation, S_tO₂) compared to the Control Group (placebo sock) at 12 weeks is superior.

Effectiveness variables will be analyzed relative to the mean of the Weekly visit 0 and -1 tissue oxygenation measurements. For purposes of statistical analysis, this mean will be referred to as the baseline.

The hypotheses are:

```
H0: %ChgPerfCelliant ≤ %ChgPerfPlacebo
Ha: %ChgPerfCelliant > %ChgPerfPlacebo
```

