A mixed model repeated measures (MMRM) will be utilized to model percent changes in tissue oxygenation by visit through 12 weeks from baseline to provide the contrast statement at 12 weeks between groups. Included in the model will be treatment group, the stratification variables of wound size (as a continuous variable) and study site. Success on this endpoint requires that the 12-week treatment group contrast difference is α <0.025. There is no interim analysis for the primary endpoint. The primary endpoint is based on a fixed study design. Regulatory activities for all but the key secondary endpoint will begin if this primary endpoint is met.

Interim Analysis for the Key Secondary Endpoint

The key secondary endpoint will only be tested for significance if the success criterion for the primary endpoint are met at the time of the primary endpoint analysis in 254 evaluable subjects, which is the interim analysis for the key secondary endpoint.

The key secondary endpoint is an inferential test of whether the Treatment Group (Celliant sock) incidence of complete wound closure rate (CWCR) compared to the Control Group (placebo sock) at 12 weeks is superior.

The hypotheses for this endpoint are:

```
H0: CWCR Celliant ≤ CWCR Placebo
Ha: CWCR Celliant > CWCR Placebo
```

The key secondary endpoint of incidence of complete wound closure at 12 weeks will be blinded except to the unblinded Interim Analysis Committee (IAC) until the final analysis for this endpoint is conducted. Since the estimated sample size for the key secondary endpoint is anticipated to be many times larger than for the primary endpoint and there is some uncertainty relative to the anticipated treatment effect, the hierarchical design allowing for the testing of the key secondary endpoint, and then the use of the adaptive group sequential design to allow for the potential of sample size re-estimation is required for efficiency.

The IAC is comprised of an unblinded statistician and a subject area medical expert whose sole responsibility is to analyze the key secondary endpoint at 254 evaluable subjects to determine, according to the Lan-Demets O-Brien Fleming alpha spending function, tested at half of the trial information:

- 1) The criterion of early stopping for efficacy for CWCR is met at half of the trial information,

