- 2) The trial will continue to the preplanned 508 planned evaluable subjects for assessing CWCR, based on the conditional power at the interim to be Cp≥ 0.85,
- 3) If neither of the first two criteria are met, then sample size re-estimation according to the inverse normal method (Lehmacher and Wassmer, 1999) will be conducted to allow for a sample size of up to 2500 evaluable subjects total for the study.
 - a. The trial will be stopped for futility of the key secondary endpoint if the Cp assuming a maximum sample size of 1250 subjects for the study provides a CP<0.7.

 - b. The trial will have a sample size increase as calculated by the inverse normal method to maintain a Cp=0.85.

With the exception of meeting criterion 1 or 3a, i.e. stopping further enrollment, the results of the interim analysis will not be shared with the clinical operations team involved directly in the study data at the patient or data management. This communication firewall is required to maintain the validity of the secondary endpoint in that subjects before and after the interim analysis are handled no differently in a way that would alter the estimated treatment effect.

A logistic model will be used to control for the stratification variables and assess for the treatment effect. Once again, as in the primary endpoint, the baseline wound size will be assessed as a continuous endpoint, although the stratification variable is dichotomous.

Type 1 error is controlled because of the hierarchical testing strategy of the primary endpoint and then key secondary endpoints, both at $\alpha_{1-\text{sided}}$ =0.025.

An Interim Analysis Charter (IAC) will be provided solely to provide a communication plan and numerical example with SAS code to detail the calculations involved for the key secondary endpoint.

Hierarchical Testing of the VAS Pain Endpoint

The VAS pain endpoint will be tested as the third hierarchical endpoint, i.e., following testing of the primary endpoint and then the total wound closure endpoint. In order for the VAS pain endpoint to be tested, the primary endpoint and the TWCR endpoints would both need to be statistically significant. The final total sample size as determined by the sample size reestimation for TWCR will be applied to the VAS pain endpoint without further modification.

Evaluability of Data

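### Futility for complete wound closure is tested at 1250 subjects against a stated cap of 2500, and the quoted power of 0.85 is not the power of the adaptive rule

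*Combined protocol and SAP*

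**What the plan says.** Four places give 2500 as the study maximum:

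- Executive Summary, Enrollment: "Enrollment may continue up to twenty-five hundred (2500) evaluable subjects total".
- Section 1, Trial Objectives: "Enrollment may include up to 2500 total subjects to meet the Key Secondary Endpoint".
- Section 4, General Statistical Considerations: "may increase up to a total of 2500 evaluable subjects".
- Section 4, Interim Analysis for the Key Secondary Endpoint, item 3: re-estimation is "to allow for a sample size of up to 2500 evaluable subjects total for the study".

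Item 3a, directly below that last statement, stops the trial for futility "if the Cp assuming a maximum sample size of 1250 subjects for the study provides a CP<0.7". Item 3b then says: "The trial will have a sample size increase as calculated by the inverse normal method to maintain a Cp=0.85".

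The interim look is at 254 evaluable subjects of a planned 508, "according to the Lan-Demets O-Brien Fleming alpha spending function, tested at half of the trial information". Item 2 continues to 508 if conditional power is at least 0.85. Otherwise item 3 applies, with the inverse normal method.

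The only power for this endpoint is in Section 4, Sample Size Justification: "at 2500 evaluable total subjects, there would be approximately a power of 0.85 to detect a difference in incidence of complete wound closure", for 25% against 20%. The plan gives no power, futility-stop probability or expected size for the adaptive rule. It does not name the effect used in the conditional power or state the stage weights.

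**The concern.** Two different study maxima sit in adjacent lines, one exactly half the other. Read literally, item 3a stops trials whose conditional power at the 2500 cap is still as high as 0.95, although item 3b accepts 0.85. The unblinded committee has to apply one reading, the decision ends enrolment, and it could not credibly be settled once closure data have been seen.

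The 0.85 describes a trial in which every subject up to 2500 is enrolled and analysed once. The specified trial can stop after 254 and gives the first 254 subjects a fixed weight however large the second stage becomes. A reader who takes 0.85 as the chance of detecting a 5-point benefit would read too much into a negative closure result. VAS pain is tested only if closure succeeds, so it inherits the same loss.

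**Working it through.** **Inputs from the plan (Section 4).** One-sided alpha 0.025; 1:1 allocation; closure 25% v 20%; interim at 127 per arm; information fraction 0.5; conditional power (CP) thresholds 0.85 (items 2 and 3b) and 0.7 (item 3a); cap 2500.

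**Assumptions.** Equal inverse-normal weights, w = √0.5, inferred from the half-information look. The CP effect is unstated, so both usual choices are shown as observed / planned. Futility is binding. Size is held at 2500 when CP of 0.85 cannot be reached. The test is an unadjusted z test, there is no attrition, and the primary endpoint has already been met.

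**1. The plan's own figure.** Variance sum 0.25×0.75 + 0.20×0.80 = 0.3475. At 1250 per arm, z = 0.05/√(0.3475/1250) = 2.999, and power = Φ(2.999 − 1.960) = 0.851. The stated 0.85 reproduces. The same formula gives 0.564 at 1250 in total and 0.272 at 508.

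**2. Bounds.** Lan-DeMets O'Brien-Fleming spending at t = 0.5 uses alpha 0.001525, so the interim bound is 2.963 and the final bound c2 is 1.969.

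**3. Interim drift.** 0.05/√(0.3475/127) = 0.05/0.0523 = 0.956.

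**4. Futility boundary.** CP = Φ(z1 − c2/w + θ√n2), with c2/w = 2.784 and n2 the second-stage subjects per arm. θ is z1/√127 (observed) or 0.05/√0.3475 = 0.0848 (planned). Set CP = 0.7, whose normal quantile is 0.524:

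- 1250 total, n2 = 625 − 127 = 498. Observed: z1 = (0.524 + 2.784)/(1 + √(498/127)) = 3.308/2.980 = 1.110. Planned: z1 = 3.308 − 0.0848×√498 = 1.416.
- 2500 total, n2 = 1250 − 127 = 1123. Observed: 3.308/3.974 = 0.833. Planned: 3.308 − 2.842 = 0.466.

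**5. Results at 25% v 20%.** The difference needed is z1 × 0.0523. The futility-stop probability is Φ(z1 − 0.956). Power is the chance of crossing 2.963 at the interim plus the integral, over continuing values of z1, of the second-stage success probability at the re-estimated size.

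| Reading of 1250 | CP effect | Boundary z1 | Interim difference needed | Futility stop | Power | Mean enrolment | Largest size |
|---|---|---|---|---|---|---|---|
| Total | observed | 1.110 | 5.8 points | 56% | 0.285 | 487 | about 1770 |
| Total | planned | 1.416 | 7.4 points | 68% | 0.278 | 552 | about 1860 |
| Per arm (2500 total) | observed | 0.833 | 4.4 points | 45% | 0.374 | 711 | 2500 |
| Per arm (2500 total) | planned | 0.466 | 2.4 points | 31% | 0.575 | 1318 | 2500 |

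Hand check of the second row: P(z1 ≥ 2.963) = 1 − Φ(2.007) = 0.022. The share continuing is 1 − 0.677 − 0.022 = 0.301, nearly all sized to CP 0.85 at the true effect. Power is therefore about 0.022 + 0.301×0.85 = 0.278.

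A one-million-run binomial simulation gives power 0.285, 0.278, 0.376 and 0.568, and futility stops of 56.0%, 67.6%, 44.8% and 32.1%.

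**6. Consequences of the two readings.**

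- Opposite decisions: 0.561 − 0.451 = 0.110 (observed), 0.677 − 0.312 = 0.365 (planned).
- CP at 2500 for a trial on the 1250-total boundary: Φ(1.110×3.974 − 2.784) = 0.948; Φ(1.416 − 2.784 + 2.842) = 0.930.
- With 1250 as the total, a trial that passes 3a never needs more than about 1770 / 1860 subjects for CP 0.85, so the 2500 cap cannot be reached.

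**7. Where the power goes.** Without a futility rule, power is 0.625 / 0.720. With every trial run to 2500 and equal stage weights it is 0.763. Neither reaches 0.85.

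**The case against.** The Sample Size Justification ties its 0.85 to 2500 subjects and never claims it for the adaptive rule. That stands: the number is correct and should stay, labelled as a fixed-design figure. It remains the only power stated, for a design the trial will not follow.

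Testing futility at a size below the re-estimation cap is a permissible choice, and a per-arm slip cannot be proved from the documents. That also stands, and so the fix asks for a clarification and does not presume the answer. But 1250 is called the maximum for the study beside a total of 2500, and on the literal reading the cap is unreachable.

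The interim charter is to detail the calculations for this endpoint with a worked example and SAS code. It might therefore settle the CP effect and the weights. It is not promised to report operating characteristics, and it cannot leave the protocol with two maxima.

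The largest contrasts come from planned-effect CP, under which item 2 would almost never apply (about 0.6% of trials at 25% v 20%, against 14.8% with observed-effect CP). On the observed-effect reading the choice moves power only from 0.285 to 0.374. That is fair on the contrast between readings, but power is far below 0.85 either way.

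Finally, the plan admits uncertainty about the effect, and a fixed 508 has 0.85 power at a difference of about 11.6 points (31.6% v 20%). Stopping early on small effects may be intended. If so, the plan should say that 5 points is not the effect this rule is powered to detect.

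**Conclusion.** The concern holds and must be fixed before the interim. The stopping rule carries two study maxima, and the stated power is not delivered on any reading. At 25% v 20%, power is 0.285 / 0.278 with 1250 as the total and 0.374 / 0.575 with 1250 per arm (CP at observed / planned effect). Power cannot exceed one minus the futility-stop probability. That alone caps it at 0.44 / 0.32 and 0.55 / 0.69.

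Read literally, a trial with exactly the planned benefit stops for futility more often than not. With control closure at 20%, the rule reaches 0.85 power only when treatment closure is 32.2% / 33.5% (1250 total) or 31.0% / 28.3% (2500 total), not 25%.

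These figures rest on the assumptions listed with the calculation, chiefly equal stage weights. Requiring the primary endpoint to succeed first could only lower power further. Type I error is not in question: simulated rejection at 20% v 20% is 0.020 to 0.022 with observed-effect CP. The primary endpoint is a fixed design and is unaffected.

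**What to change.** 1. In the Sample Size Justification, label 0.85 as the power of a fixed 2500-subject comparison. Add the simulated power and futility-stop probability of the actual rule at 25% v 20%.
2. Before the unblinded interim, reconcile the 1250 in item 3a with the 2500 total by stating whether 1250 is per arm or total.
3. State the effect used for conditional power and the pre-fixed stage weights, since the figures in (1) depend on them.

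The futility threshold and the weights remain the sponsor's choice.

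Items 1 and 3 cost a short simulation, some SAP wording and a less favourable stated power. Item 2 depends on the answer. If it is 2500 total, expected enrolment at 25% v 20% rises from about 487 to 711 (observed-effect CP) or from about 552 to 1318 (planned-effect), and the largest size rises from about 1770 or 1860 to 2500, all within the cap already stated. If it is 1250 total, enrolment does not change, but a power of about 0.28 must be stated.

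### VAS pain is a confirmatory endpoint whose look and sample size follow unblinded closure results, yet it has no boundary or combination rule, so one-sided 0.025 is not guaranteed

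*Combined protocol and SAP*

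**What the plan says.** All references are to Section 4, Statistical Analyses.

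- **Hierarchical Testing of the VAS Pain Endpoint.** VAS comes third. For it to be tested, "the primary endpoint and the TWCR endpoints would both need to be statistically significant" (TWCR is the closure endpoint). On sample size, the total that the closure re-estimation produces "will be applied to the VAS pain endpoint without further modification".
- **Interim Analysis for the Key Secondary Endpoint.** Closure is examined by an unblinded committee at 254 evaluable subjects under a Lan-DeMets "O-Brien Fleming alpha spending function, tested at half of the trial information". The trial can stop for efficacy, continue to 508, stop for futility, or undergo "sample size re-estimation according to the inverse normal method" up to 2500. These safeguards are stated for closure only, and the interim charter is likewise confined to the key secondary endpoint.
- **Same subsection, on error control.** "Type 1 error is controlled because of the hierarchical testing strategy of the primary endpoint and then key secondary endpoints". One-sided 0.025 is attached to those two endpoints; VAS is not named.
- **General Statistical Considerations.** "The p-value thresholds for determining statistical significance are 0.05 and 0.025 for 2- and 1-sided tests", unless specified otherwise. This is the only level in the plan that can apply to VAS.

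**The concern.** Testing endpoints in a fixed order at full alpha is valid when each endpoint has one fixed analysis. Here the gate to VAS can open at either of two looks, and the second look has a size chosen from interim data. If VAS is compared with 1.96 whenever closure succeeds, the closure result chooses which VAS analysis counts. When the two endpoints are correlated, that choice favours looks at which VAS is high by chance.

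Some correlation is plausible from the documents themselves. The VAS rates pain in the same study wound whose closure is tested, and the device description ties closure and possible pain reduction to one mechanism. At stake is a pain claim: pain appears in the proposed indications for use, and it would rest on a nominal level that the design may not deliver.

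**Working it through.** **1. The plan's own figures.**
- Primary: n per arm = 2 × 21.7² × (1.960 + 1.036)² / 8.2² ≈ 126, or 252 in total; power at 127 per arm is 0.853. This agrees with the stated 254 and 0.85.
- Closure: 25% versus 20% with 1250 per arm gives power 0.850, as stated.
- The documents give no power or error figure for VAS.

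**2. Closure boundary.** Lan-DeMets O'Brien-Fleming, one-sided 0.025, information fraction 0.5: c1 = 2.963 (alpha spent 0.0015) and c2 = 1.969.

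**3. Decision zones at 254.** Assume conditional power under the observed trend, equal inverse normal weights, and the futility figure of 1250 read as total subjects. With z1 the closure statistic at 254:

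CP(N) = Φ( z1 + z1·√((N − 254)/254) − 1.969·√2 ), where 1.969·√2 = 2.784.

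- CP ≥ 0.85 at 508: 2·z1 ≥ 2.784 + 1.036, so z1 ≥ 1.910.
- CP < 0.7 at 1250: z1·(1 + √(996/254)) < 2.784 + 0.524, so z1 < 1.110.

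So closure stops for efficacy above 2.963, goes to 508 between 1.910 and 2.963, is enlarged between 1.110 and 1.910, and stops for futility below 1.110.

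**4. Planned closure effect on this scale.** 0.05 / √(2 × 0.225 × 0.775 / 127) = 0.954.

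**5. VAS error.** Simulation with 2 million trials per cell: VAS has no true effect, is tested only if closure is significant, and is compared with 1.96 on the pooled data. The oxygenation gate is taken as always passed. The correlation ρ is assumed. Figures are good to about 0.001.

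| ρ | Worst case, futility applied | Worst case, futility not enforced | 25% vs 20%, futility applied | 25% vs 20%, not enforced |
|---|---|---|---|---|
| 0 | 0.025 | 0.025 | 0.007 | 0.016 |
| 0.3 | 0.027 | 0.029 | 0.014 | 0.024 |
| 0.5 | 0.029 | 0.032 | 0.019 | 0.029 |
| 0.7 | 0.032 | 0.036 | 0.026 | 0.035 |

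Hand check at ρ = 0: the error is 0.025 × P(closure significant). At the planned effect with futility applied this is 0.025 × 0.282 = 0.007, as tabulated.

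**6. Source of the excess.** With looks at 254 and 508 only and no re-sizing, the maximum is already 0.027 at ρ = 0.3 and 0.031 at ρ = 0.7. Most of the excess therefore comes from using 1.96 at whichever look closure selects; pooling after re-sizing adds less.

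**7. Candidate repairs (futility not enforced).**

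| VAS test | Maximum error |
|---|---|
| Inverse normal statistic, still 1.96 at either look | 0.031 at ρ = 0.7 |
| O'Brien-Fleming bounds on pooled data | 0.027 |
| O'Brien-Fleming bounds on inverse normal statistic | 0.021 for ρ up to 0.7; 0.025 at ρ = 1 |
| Pocock bounds (2.178) on inverse normal statistic | 0.024 |

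The last two are also safe by argument. Under no VAS effect, the stage-one and combined statistics keep their planned joint distribution however closure sets the second-stage size. The chance of crossing either bound is then 0.025, and the closure gate can only remove rejections.

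**The case against.** **The plan does not say that VAS data will be pooled without adjustment, and its VAS paragraph names no level.** This stands. A reader might infer that VAS is tested at full one-sided 0.025 on naively pooled data and that its error therefore exceeds 0.025. The documents do not support that. Pooling is an inference from silence, the level comes from a general default that yields to any later specification, and the sentence on type I error claims nothing for VAS. What is established is an unspecified test under a closure-driven look and size.

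**The excess is conditional.** This stands too. It vanishes at ρ = 0. At the planned closure effect with futility applied, it appears only near ρ = 0.7. The worst cases for ρ = 0.3 and 0.5 sit at a mean closure Z of about 2.75 and 2.25 at 254 subjects, roughly 35% and 32% closure against 20%, or about 2.5 to 3 times the planned difference. But control has to hold at every closure effect, and the plan itself admits uncertainty about that effect.

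**Extreme correlations should not be headline figures.** Errors of 0.042 to 0.048 arise at ρ = 1. If VAS change is roughly normal, its correlation with a binary endpoint at rates of 20% to 25% cannot exceed φ(z)/√(p(1 − p)), which is 0.70 to 0.73. Those figures are set aside.

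**The oxygenation gate lowers the error.** If that gate is passed with probability 0.85, independently of the other endpoints, 0.027 becomes 0.027 × 0.85 = 0.023 and 0.029 becomes 0.025. This reduces the realistic size but does not restore a guarantee, because the gate may be passed almost surely.

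**Conclusion.** The point holds as a lack of guaranteed control. VAS is formally confirmatory, its look and size are set by unblinded closure results, and the plan supplies neither a boundary nor a combination rule. Applying the default 1.96 can give a one-sided error above 0.025: at worst about 0.027 to 0.032 for ρ of 0.3 to 0.7 with futility applied, and 0.029 to 0.036 if it is not enforced.

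These figures rest on an assumed positive correlation, a passed oxygenation gate, observed-trend conditional power and unadjusted pooling. The excess is modest and affects only the third-ranked endpoint; the plan's statement on closure is not called into question here.

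**What to change.** In the VAS paragraph, replace the clause that carries the closure sample size over unchanged with a testing rule:

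- State the VAS level (one-sided 0.025) and its own pre-specified two-look alpha-spending boundary. One example is O'Brien-Fleming, 2.963 at 254 and 1.969 at the final look; a Pocock-type boundary of 2.178 at both looks is an alternative.
- Apply that boundary to the stagewise inverse normal VAS statistic, with the same pre-fixed weights as closure. Neither element is sufficient alone.
- Extend the type I error statement and the interim charter to cover VAS.

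The cost is SAP wording, with no added subjects. The downside is a larger z for VAS if closure stops at the interim, most marked under O'Brien-Fleming. At the final look the O'Brien-Fleming critical value barely moves (1.960 to 1.969), whereas Pocock eases the interim hurdle and raises the final one. The choice between them is a design preference.
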